4.3 Potential Influencing or Confounding Factors and Bias

Another potential foreseeable factor pertains to the global nature of this investigation and the varying practice patterns across the regions that may participate. These differences could stem for example from differing surveillance programs, differing criteria for initiating CVC hemodialysis, among others. This factor is mitigated through CIP stipulated training requirements, as well as maximum enrollment limitations on any single site, and standardization for follow-up interval timing and pertinent requirements. Subgroup analyses between regions may be conducted to explore regional differences for standard of care differences. This could also be expanded to inter-region subgroup analyses should there be differences in institution types (e.g. public versus private) that participate within a region.

In addition to region and institution type, the training and level of experience with the Pristine™ Long-Term Hemodialysis Catheter as well as the specialty of the operator could also be a foreseeable factor that could impact the study outcomes. As a mitigation of this factor the training and operator approval requirements delineated in Section 13.2 are implemented. Subgroup analyses looking at the experience level and / or specialty of the operator may also be performed to investigate the impact on results.

4.4 End of Study Definition

A participant is considered to have completed the study upon conclusion of the 12-Month (± 1 month) follow-up visit. The end of the study is defined as the date of the last visit of the last participant in the study.

5 STUDY POPULATION

Study population includes participants with end stage renal disease requiring hemodialysis through a tunneled dialysis catheter. All participants must meet all inclusion and exclusion criteria.

Participants will be recruited for enrollment in the study from each site's existing pool of patients. Enrollment of participants will continue until a total of 142 patients at up to 15 sites have been enrolled and undergo the placement procedure successfully of the BD Pristine™ Long-Term Hemodialysis Catheter. It is anticipated that enrollment will be approximately 12 months in duration. The following describes the clinical eligibility (inclusion and exclusion) criteria for this study:

5.1 Inclusion Criteria

In order to be eligible to participate in this study, an individual must meet all of the following criteria:

1. The participant or legally designated representative must voluntarily sign and date the approved Informed Consent Form (ICF) prior to collection of study-specific data or performance of study-specific procedures.
2. The participant must be willing and able to comply with protocol requirements, including all study visits and procedures.
3. The participant must be either a male or non-pregnant female ≥ 18 years of age.
4. The participant must have a diagnosis of End Stage Renal Disease with indication for a tunneled dialysis catheter creation.
5. Participant must require chronic hemodialysis treatments 3 times per week with intended use of the Pristine™ Long-Term Hemodialysis Catheter.
6. The participant meets the indications for hemodialysis use and does not meet any of the contraindications per the Pristine Instructions for Use (IFU).
7. The participant must have a patent jugular vein or subclavian vein.

5.2 Exclusion Criteria

A participant must NOT meet ANY of the following criteria to be enrolled in the study:

1. The participant has known central venous stenosis
2. Based on the local primary investigator's discretion, the patient would not be an appropriate study candidate.

3. The participant has already undergone an AVF or AVG procedure and is awaiting maturation.
4. The participant has an active infection at the time of study enrollment.
5. The participant has a presence of bacteremia or infection within 7 days prior to enrollment.
6. The participant has a history neutropenia or a history of severe immunodeficiency disease.
7. The participant has uncontrolled abnormal coagulation parameters and are at additional risk for clotting or excessive bleeding at time of enrollment per physicians' opinion.
8. The participant has a known allergy, intolerance or sensitivity to heparin, or previous incidence of heparin-induced thrombocytopenia.
9. The participant has a known allergy or hypersensitivity to any of the device materials or Ethylene oxide (EtO).
10. The participant has another medical condition or treatment, which in the opinion of the investigator, the participant may be non-compliant with the protocol, confound the data interpretation, or is associated with a life expectancy insufficient to allow for completion of study procedures and follow-up.
11. The participant is currently participating in an investigational drug or another device study that has not completed the study treatment or that clinically interferes with the study endpoints. Note: Studies requiring extended follow-up visits for products that were investigational but have since become commercially available, are not considered investigational studies.

5.3 Lifestyle Considerations

No lifestyle restrictions are required for this study.

5.4 Screen Failures

Individuals that consent to participate in the study but subsequently fail to meet eligibility criteria and do not undergo treatment with the study device at the Index Procedure will be considered SCREEN FAILURES. Study participation for screen failures will end at the time of

eligibility failure and these individuals may not be rescreened. Documentation of the reason(s) for screen failure should be present in the participant's medical record and/or source documents.

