7.1.2 Enrolled Participants

Individuals that consent to participate in the study will be considered **ENROLLED**. Participants that fail to meet eligibility criteria post-consent and prior to undergoing device placement with the study device will be considered **SCREEN FAILURES** per Section 5.4.

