## 4 Analysis Population Set(s)

### 4.1 Population Definitions

The following populations are defined:

Table 2: Analysis Population List

Population	Description
Enrolled	All participants who sign the ICF will be classified as enrolled.
Intent-to-Treat (ITT)	
The ITT population will consist of all participants who have signed the ICF, met all inclusion/exclusion criteria, and had the procedure initiated.
 
The ITT population includes the following three groups on the Subject Disposition CRF page: Eligibility met but device not inserted, Device inserted but subject did not undergo first dialysis session, and Treated with study device.

Modified Intent-to-Treat (mITT)	
The mITT population will consist of all ITT participants treated with the study device.
 
The mITT population includes subject treated with study device on the Subject Disposition CRF page.

Per-Protocol (PP)	
A PP population may be created if there are participants who have any major deviations. The PP population will consist of any participants in the mITT population who do not have any major deviations. The deviations that are considered to have a “major” grade will be identified and summarized in Appendix 3 prior to data analyses.

All endpoints will be analyzed primarily based on the mITT population and ITT population where applicable. PP analyses may also be performed for the primary endpoints and will only serve as sensitivity analyses.

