### **5.3.3 Rate of Technical Success, defined as the successful placement of the Pristine™ Long-Term Hemodialysis Catheter, as assessed by the Investigator during the Index Procedure.**

Subject will be considered as having technical success if the subject has experienced successful placement of the catheter at the intended site during the procedure:

- **Procedure Overview Part-1 CRF Page:** Was there successful placement at the intended site of the Pristine™ Long-Term Hemodialysis Catheter: Equals Yes

The rate of technical success will be reported with 95% confidence interval from the exact binomial method. The analysis will be performed on the ITT population.

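### Screen failure stays open until the device is placed, not until skin puncture, so some failed placement attempts can be relabelled as ineligible and leave the Technical Success denominator.

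*Protocol*

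**What the plan says.** **Screen failure.** Protocol 5.4 covers consented individuals who "subsequently fail to meet eligibility criteria and do not undergo treatment with the study device at the Index Procedure will be considered SCREEN FAILURES", and ends their participation when eligibility fails. Protocol 7.1.2 gives the time limit: "Participants that fail to meet eligibility criteria post-consent and prior to undergoing device placement with the study device will be considered" screen failures. SAP 2.6 repeats it.

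**Start of the procedure.** Protocol 7.3 dates the index procedure from the first skin puncture made to reach the vessel. The interval from puncture to placement therefore lies inside the screen-failure window.

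**Criteria that an attempt can touch.** Inclusion 7 reads "The participant must have a patent jugular vein or subclavian vein". Exclusion 2 reads "Based on the local primary investigator's discretion, the patient would not be an appropriate study candidate".

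**Populations.** SAP 4.1 limits ITT to participants who signed consent, "met all inclusion/exclusion criteria, and had the procedure initiated". It names three disposition groups, one of them eligible participants in whom no device was inserted. For Technical Success, SAP 5.3.3 states: "The analysis will be performed on the ITT population". SAP ITT is also the population for kit-component complications (SAP 5.4), one of the 1-month analyses of related adverse events (SAP 5.3.2) and the adverse event summaries (SAP 7). Protocol Table 5 differs: its ITT requires that the catheter was placed, and Protocol 10.6 uses that ITT for the secondary endpoints.

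**The concern.** Technical Success should be counted over everyone in whom placement was attempted. Here a finding made during the attempt can decide whether the participant is counted.

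The gap is reachable in practice. The Schedule of Activities lists no imaging, the required physical examination names only height and weight (Protocol 7.1.4), and no laboratory tests are required (7.1.5). Patency may therefore first be tested when the operator tries to gain access. Exclusion 2 rests on investigator judgement and states no time limit.

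At stake are the reported Technical Success rate and the ITT safety summaries for the procedure. A participant who was punctured but received no catheter can still have had a procedural complication. Protocol section 3 says the results are intended for the device labeling, so even a descriptive rate needs a denominator that the outcome cannot change.

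**Working it through.** The documents give no Technical Success rate, target or expected number of failed attempts, so there is no planned figure to reproduce. The check has two parts.

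**1. Where a failed attempt goes (no catheter placed, skin already punctured)**

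| Finding during the attempt | Eligibility | SAP ITT | Protocol ITT (Table 5) |
|---|---|---|---|
| No patent jugular or subclavian vein; inclusion 7 judged not met | Not met | Dropped as screen failure | Dropped |
| Re-judged unsuitable under exclusion 2 | Not met | Dropped as screen failure | Dropped |
| Target vein unusable, another listed vein patent | Still met | Kept, Technical Success = No | Dropped |
| Central stenosis first found at the procedure | Still met | Kept, Technical Success = No | Dropped |
| Passage fails for another reason | Still met | Kept, Technical Success = No | Dropped |

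Under the SAP, only the first two rows leave the denominator. Under the protocol every row leaves it, because Table 5 requires placement. Technical Success on the protocol's ITT is then close to 100% by construction.

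**2. Size of the effect under the SAP**

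Inputs: S = 142 successful placements (the enrolment target in Protocol section 5); k = attempts relabelled as screen failures (assumed); f = failed attempts that stay in ITT (assumed). Intervals are exact binomial, the method in SAP 5.3.3, with lower limit Beta(0.025; x, n−x+1) and upper limit Beta(0.975; x+1, n−x).

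- Rate as reported: S / (S + f)
- Rate with every initiated procedure counted: S / (S + f + k)

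With f = 0 the reported result is 142/142 = 100% for any k. Its lower limit is 0.025^(1/142) = 0.974, so the interval is 97.4 to 100. With all attempts counted:

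| k | Rate | Exact 95% CI |
|---|---|---|
| 1 | 142/143 = 99.3% | 96.2 to 100.0 |
| 3 | 142/145 = 97.9% | 94.1 to 99.6 |
| 7 | 142/149 = 95.3% | 90.6 to 98.1 |

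If some failures stay in ITT the gap is much the same. With f = 3 and k = 3, the report would show 142/145 = 97.9% against 142/148 = 95.9%, a difference of 2.0 percentage points.

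**The case against.** A reader might infer that any attempt defeated by an unusable vein automatically becomes a screen failure. The documents do not say that, and the case against this reading is strong.

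- Screen failure needs two things: an eligibility failure and no treatment. A failed attempt supplies only the second.
- One patent jugular or subclavian vein satisfies inclusion 7, so an unusable target vein need not breach it. The stenosis criterion is "The participant has known central venous stenosis", so stenosis discovered at the procedure does not exclude.
- Protocol 7.1.6 and 7.2.1 put the eligibility decision before treatment, and Protocol 7.1.1 lets routine imaging obtained before consent serve for screening.
- Failed attempts have their own routes: Protocol 7.2.1 when no catheter is introduced, and 7.4.1 when it is introduced without procedure success. SAP ITT keeps eligible participants without an inserted device.
- SAP 6.1 tabulates screen failures by unmet criterion, so relabelling would be visible. SAP 7 lists all adverse events.
- The documents give no causes of failed placement, so they do not support calling a non-patent vein a main cause. Continuing enrolment to 142 successful placements does not by itself bias the rate.

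Most of this stands, and it confines the concern to the first two rows of the table above. It does not remove it. Protocol 7.1.6 ties the documentation to treatment and not to puncture, neither 7.1.6 nor 7.2.1 says that a later finding cannot reverse the decision, and routine imaging is allowed but not required. The separate SAP group protects only participants still regarded as eligible.

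**Conclusion.** The concern holds in a limited form. Because the window closes at placement and SAP ITT requires all criteria to be met, an attempt that shows no patent jugular or subclavian vein, or that prompts a post-puncture judgement under exclusion 2, can be removed from Technical Success, kit-component complications and the ITT adverse event analyses.

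Upward bias in Technical Success is possible, not certain, and its size is unknown. It depends on how many attempts are relabelled, which the documents do not let anyone estimate. Three relabelled attempts with no other failures would move the rate by about 2 percentage points (100% reported, 97.9% if counted). The 142/142 result is an illustration that assumes every failure is relabelled; the documents do not support it as the expected outcome.

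Technical Success is descriptive (Protocol 10.6), so no hypothesis test or type I error is involved. The primary analysis uses the SAP's mITT population of treated participants and is unaffected. The same edit should settle the conflict between the two ITT definitions, since the protocol's version drops every failed placement whatever the screen-failure rule says.

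**What to change.** 1. In Protocol 5.4 and 7.1.2 and SAP 2.6, allow screen failure only before the initial skin puncture, the time point already defined in Protocol 7.3.
2. In SAP Table 2, define ITT as consent signed, judged eligible before skin puncture, and procedure initiated. Later findings then cannot remove a participant.
3. Replace the placement requirement in the ITT row of Protocol Table 5 with the same definition.
4. In SAP 5.3.3, score Technical Success as No for every initiated procedure without successful placement.
5. Reconcile Protocol 7.2.1, which ends participation at the index procedure when no catheter is introduced, with the 1-month ITT analysis of related adverse events in SAP 5.3.2. State that related events recorded from puncture onward count in ITT.

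The cost is a few lines in each document. Exclusions made before puncture, including on ultrasound, are unaffected. The downside for the sponsor is a slightly lower reported Technical Success rate if such cases occur.

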6 STUDY TREATMENT

All participants will undergo a clinical evaluation at the Screening Visit (prior to Index Procedure). Participants that meet Eligibility Criteria will have the BD Pristine™ Long-Term Hemodialysis Catheter placed and will undergo additional follow-ups. Follow-up for all enrolled participants will be performed via in-person or telephone screen to the participant and dialysis center at 1-month, 3-months, 6-months, and 12-months post-Index Procedure.

6.1 Pristine™ Long-Term Hemodialysis Catheter

The Pristine™ Long-Term Hemodialysis Catheter is a chronic hemodialysis catheter consisting of a dual lumen radiopaque shaft with a pre-formed split tip, which enables long-term vascular access for hemodialysis, apheresis, and infusion. The proximal end of the catheter features two color coded luer adapters. The luer adapters are connected to clear extension tubes. Each extension tube contains a clamp and is connected to the catheter bifurcation and suture wings (hub). The distal end of the catheter hub is connected to the dual lumen catheter shaft. The shaft contains a cuff and extends to a symmetrical split tip. The design of the catheter's distal tip includes a split, symmetric Y-Tip™ with notches and without side-holes or slots. The symmetric Y-Tip™ design allows a spatial separation between the distal ends of the two lumens. The Pristine™ Long-Term Hemodialysis Catheter is provided as a sterile, single use device, and is sterilized using a validated ethylene oxide process.

The Pristine™ Long-Term Hemodialysis Catheter is FDA cleared and will be evaluated in a post-market fashion for its approved indication in the USA. Sites are to use the product off-the-shelf. The product shall be used in accordance with its IFU. The device will be identified using its product code and lot number for traceability. Please refer to the standard medical device reporting for any failed or malfunctioned Pristine™ Catheters.

7 STUDY PROCEDURES AND ASSESSMENTS

Study procedures, assessments, and their timing are summarized in the Schedule of Activities (SoA) in Section 1.2. Protocol waivers or exemptions are not allowed. Adherence to the study design requirements, including those specified in the SoA, is essential and required for study conduct. All study procedures must be documented in the participant's medical record and/or source documents as well as in the electronic Case Report Forms (eCRFs).

Prior to the collection of any study-specific data, the participant must voluntarily sign and date the IRB approved ICF. All participants will undergo an in-office clinical evaluation at the Screening Visit (prior to Index Procedure). Participants that meet Eligibility Criteria will be treated with the Pristine™ Long-Term Hemodialysis Catheter and will undergo additional follow-ups. Follow-up for all enrolled participants will be performed via in-person or telephone screen to the participant and dialysis center at 1-month, 3-months, 6-months, and 12-months post-Index Procedure.

7.1 Screening and Enrollment

During the recruitment and screening process, the Investigator (or authorized designee) will be responsible for describing the nature of the study to the participant, verifying that initial eligibility criteria have been met, obtaining Informed Consent, collecting participant information, and performing relevant screening procedures. The following procedures will be conducted and documented during the screening process:

7.1.1 Informed Consent

The background and purpose of the study, participation requirements, and the potential benefits and risks of the procedure(s) must be explained to the participant in layman's terms. Prior to the collection of any study-specific data or the conduct of any protocol-specific assessments, the participant or the legally designated representative must voluntarily provide Informed Consent and comply with applicable federal and state privacy laws (e.g. HIPAA requirements in the US). Documentation of the Informed Consent process along with the signed Informed Consent Form should be present with the participant's source documents and dated prior to initiation of study-specific assessments. Procedures conducted as part of the participant's routine clinical management (e.g. imaging, labs, etc.) and obtained before signing of the ICF may be utilized for Screening purposes provided the procedures meet the protocol-specified criteria and were performed within the time frame defined in the SoA. Please refer to Section 14.2 for additional details on informed consent.

7.1.2 Enrolled Participants

Individuals that consent to participate in the study will be considered **ENROLLED**. Participants that fail to meet eligibility criteria post-consent and prior to undergoing device placement with the study device will be considered **SCREEN FAILURES** per Section 5.4.

7.1.3 Demographics and Medical History

The following demographic and medical history information must be collected and documented during the Screening Visit:

- Demographics

- Age, Sex, Race, and Ethnicity
- Relevant Medical History and Risk Factors including, but not limited to:
 - Renal disease Diagnosis
 - Etiology of End-Stage Renal disease
 - History of kidney-related medical conditions, treatments, and procedures.
 - History of other relevant medical conditions, treatments, and procedures.

7.1.4 Physical Exam

A physical examination must be conducted or documented within 30 days prior to Index Procedure in accordance with each investigational site's standard of care and must include:

- Height and Weight

7.1.5 Lab Tests

No lab tests are required for study participation.

7.1.6 Eligibility Assessment

The participant's eligibility for treatment with Pristine™ Long-Term Hemodialysis Catheter will be reviewed and source documentation should indicate that the participant met all study eligibility criteria prior to the Index Procedure treatment. Refer to Section 5.4 if eligibility criteria are not met.

7.2 Index Procedure Visit

The Index Procedure should be conducted per the investigational site's standard practices for hemodialysis catheter procedures, medication therapy, patient monitoring, sterile operative techniques, and within the bounds and requirements of the Pristine™ Long-Term Hemodialysis Catheter IFU. The following must be documented at the Index Procedure Visit:

7.2.1 Clinical Procedure

After the PI, or authorized designee(s), has determined that the participant is eligible for participation based on the criteria listed in Section 5.1 and 5.2, the participant may be enrolled and undergo the Pristine™ Catheter placement procedure. Examinations, evaluations, procedural preparation, angiography, treatment, and hospital / facility discharge procedures will be conducted per the investigational site's SOC.

The placement of the Pristine™ Catheter, will be per the investigational site's SOC and must adhere to the device IFU. Operators of the Pristine™ Catheter must be approved by the Sponsor as an operator in writing before conducting an index procedure on enrolled participants (refer also to Section 13.3). For detailed information on device use and procedural medication recommendations, reference the IFU.

Enrolled participants will continue clinical participation through the 12-month follow-up period. Participants into whom the Pristine™ Catheter was not introduced should be treated per SOC and the reason documented on the appropriate eCRF. Participation for these participants will end at time of the index procedure.

